14.1 Primary Endpoint: Confirmed Objective Response

Primary endpoint is the confirmed objective response according to Response Evaluation Criteria in Solid Tumors Version 1.1 (RECIST 1.1) assessed by an IRC.

14.1.1 Primary Objective: Derivation and Analysis of the Primary Endpoint Confirmed Objective Response

Best Overall Response

Best overall response (BOR) will be assessed based on reported overall responses at different evaluation time points from the treatment start date until documented disease progression in accordance to RECIST v1.1, taking requirements for confirmation into account as detailed below. Only tumor assessments performed before the start of any subsequent anti-cancer therapies will be considered in the assessment of BOR. If a tumor assessment was performed on the same day as start of new anti-cancer therapy, it will be assumed that the tumor assessment was performed prior to the start of the new anti-cancer therapy, therefore the tumor assessment will be included in the assessment of BOR. Clinical deterioration will not be considered as documented disease progression. The date of the overall response assessment is the earliest date for imaging of target, non-target and new lesions of images taken at that response assessment.

BOR can be defined as confirmed or unconfirmed, both definitions are provided below.

Confirmed Best Overall Response (cBOR)

- CR = at least two determinations of CR at least 4 weeks apart (with no PD in between).
 - Note: Assessments with results CR-NE-CR, with NE as not evaluable, or CR-PR-CR will be considered as CR as long as the second CR is more than 28 days away from the first timepoint.
- PR = at least two determinations of PR or better (PR followed by PR or PR followed by CR) at least 28 days apart (and not qualifying for a CR), with no PD in between.
 - Note: Assessments with results PR-NE-PR or PR-SD-PR will be considered PR as long as the second PR is more than 28 days away from the first timepoint.

- SD (applicable only to participant with measurable disease at baseline) = at least one SD assessment (or better) \geq 6 weeks, after start date and not qualifying for CR or PR.
- Non-CR/non-PD (applicable only to participants with non-measurable disease at baseline) = at least one non-CR/non-PD assessment (or better) \geq 6 weeks after start date (and not qualifying for CR or PR).
- PD = PD \leq 12 weeks after start date (and not qualifying for CR, PR, non-CR/non-PD or SD).
- Not Evaluable (NE): all other cases.

Unconfirmed Best Overall Response (uBOR)

uBOR according to RECIST 1.1 as adjudicated by IRC will be assessed according to the following rules:

- CR = at least one assessment of objective status of CR documented before progression.
- PR = at least one assessment of objective status of PR documented before progression (and not qualifying for CR).
- SD (applicable only to participant with measurable disease at baseline) = at least one SD assessment (or better) \geq 6 weeks after start date and before progression (and not qualifying for CR or PR).
- Non-CR/non-PD (applicable only to participants with non-measurable disease at baseline) = at least one non-CR/non-PD assessment (or better) \geq 6 weeks after start date and before progression (and not qualifying for CR or PR).
- PD = progression \leq 12 weeks after start date (and not qualifying for CR, PR, SD or non-CR/non-PD).
- NE: all other cases.

Objective Response (OR)

The Objective Response (OR) is defined as a BOR of CR or PR according to RECIST v1.1.

Participants who do not have an on-treatment radiographic tumor assessment due to early progression, who receive anti-tumor treatments other than the study treatments prior to reaching confirmed CR or PR, or who die, progress, or drop out for any reason prior to reaching confirmed CR or PR will be counted as non-responders in the assessment of OR. Each participant will have an objective response status (0: 'no OR'; 1: 'OR').

Objective Response Rate (ORR)

The ORR is defined as the number of participants having an OR assessment of CR or PR (responders), out of the total number of participants in the analysis set.

Confirmed ORR will be determined as the proportion of participants in the analysis set with a confirmed OR of PR or CR (having at least two determinations of CR/PR at least 4 weeks apart and before progression).

The confirmed ORR according to RECIST 1.1 as assessed by the IRC is the primary endpoint of the study. The study aims to estimate the ORR with a sufficient level of precision and that the associated two-sided 95% CI is above a minimal threshold of 10%.

Disease Control Rate (DCR)

Disease Control Rate (DCR) is defined as the proportion of participants with BOR according to evaluation criteria of CR, PR, or SD out of the total number of participants in the analysis set.

Details of analyses

Separate tables will be provided for confirmed and unconfirmed BOR. Each one will provide the number and percentage of participants with cBOR (respectively uBOR) of CR, PR, SD, PD and NE as well as the ORR and the DCR. The ORR and DCR will be provided with a two-sided 95% CI using the Clopper-Pearson method (exact CI for a binomial proportion as computed by default by the FREQ procedure using the EXACT option).

The individual percentage of change in the sum of diameter since baseline will be displayed over time on a spider plot, together with the first occurrence of new lesion, the participant off treatment and the start of subsequent anticancer treatment. The curves will be color-coded to differentiate responder vs non-responder subjects.

The change in the sum of diameters between baseline and the best post-baseline assessment (i.e. maximum tumor shrinkage) will be displayed on a waterfall graph. The sum of diameters includes all target lesions (longest diameter for non-nodal lesions and short axis for nodal target lesions).

For spider plots and waterfall plots, the percent change from baseline in the sum of diameters will be displayed for valid timepoint assessments, only. For the purpose of this analysis, a valid timepoint assessment is defined as a complete assessment of all target lesions reported at baseline. Further, split and coalesced lesions have to be taken into account appropriately to determine if a timepoint assessment is valid to derive the percent change from baseline in sum of diameters. All sum of diameters will be used, including the ones beyond first PD (for waterfall plot, the best post-baseline sum of diameters will be used even if occurring beyond PD). For waterfall plot, the percent change from baseline to 8-weeks assessment, as well as the percent change from baseline to the best post-baseline sum of diameters will be displayed for each participant.

Two listings of tumor assessment will be provided with the following information:

- First listing will display participant identifier, age, sex, race, first and last date of treatment, date of start of subsequent anticancer therapy, date of death when death occurs, visit, date(s) of imaging, description of target lesions (size, site, type, method), non-target lesions (status, site, type, method), and new lesions (site, type, method) and if the lesion split or merged. This listing will be sorted by participant identifier, visit, date of imaging, lesion type (TL, NTL, NEW) and lesion ID.

- Second listing will present participant identifier, age, sex, race, first and last date of treatment, cBOR, uBOR, date of start of subsequent anticancer therapy, date of death when death occurs, target response, non-target response, new lesion, sum of diameters, % of change in sum of diameters since baseline and overall response. This listing will be sorted by participant identifier, visit and date of imaging.

In addition, a summary table of the reasons for non-evaluable confirmed BOR will be provided, the following reasons will be detailed:

- No baseline assessment (if applicable)
- No post-baseline assessments due to death within 8 weeks after the start of study treatment
- No post-baseline assessments due to other reasons
- All post-baseline assessments have overall response 'Non-evaluable'
- New anticancer therapy started before first evaluable post-baseline assessment
- SD of insufficient duration (< 6 weeks after the start of study treatment)
 - Note: Special cases where BOR is NE due to both early SD and late PD will be classified into this category
- No evaluable tumor assessment > 16 weeks followed by PD (i.e. tumor assessment of PD was > 16 weeks after start of study treatment and there was no evaluable tumor assessment in between)
- No IRC review and Not determined categories may also be added if applicable

A listing of reasons for non-evaluable confirmed BOR will also be created including: participant identifier, age, sex, race, date of first and last dose, date(s) of imaging, overall response and the reason for confirmed BOR non-evaluable.

14.1.2 Subgroup Analysis of the Primary Endpoint Confirmed Objective Response

Confirmed BOR, ORR and DCR according to RECIST 1.1 as adjudicated by IRC will also be evaluated on all subgroups as defined in section 8.2.

Participants with missing subgroup category will not be included in the related subgroup analysis. Response rates and corresponding 95% CI of all subgroups will be presented in a forest plot together with the respective results for the primary analysis set. Corresponding efficacy tables will not be provided.

No adjustment for multiplicity will be performed.

14.2 Secondary Endpoint: Objective Response According to RECIST 1.1 as Assessed by Investigator

[figure not shown]
Data collected in the eCRF for RECIST 1.1 response criteria as assessed by the Investigator ("Assessment of disease based on imaging (according to RECIST 1.1)" eCRF page) will be treated

in the same way as data adjudicated by the IRC. Analyses described in section 14.1.1 will be repeated based on Investigator assessment, i.e.:

[figure not shown]
- Number and percentage of participants with confirmed BOR of CR, PR, SD, PD and NE and corresponding listing. Analyses will be repeated for unconfirmed BOR
- ORR and DCR with their two-sided 95% CI. Analyses will be repeated for unconfirmed BOR
- Spider and Waterfall plots
- A summary table of the reasons for non-evaluable confirmed BOR and related listing, with the following reasons:
 - No baseline assessment (if applicable)
 - No post-baseline assessments due to death within 8 weeks after the start of study treatment
 - No post-baseline assessments due to other reasons
 - All post-baseline assessments have overall response 'Non-evaluable'
 - New anticancer therapy started before first evaluable post-baseline assessment
 - SD of insufficient duration (< 6 weeks after the start of study treatment)
 - No evaluable tumor assessment > 16 weeks followed by PD (i.e. tumor assessment of PD was > 16 weeks after start of study treatment and there was no evaluable tumor assessment in between)
 - Not determined category may also be added if applicable
- Listing of reasons for non-evaluable confirmed BOR
- Listing of individual tumors assessment as well as of time point tumor response and overall response

In addition, a summary of the BOR (confirmed and unconfirmed) as adjudicated by IRC versus Investigator assessment will be provided including numbers of concordant and discordant assessments, and a listing of inconsistencies will be provided.

CCI

CCI

CCI

14.4 Secondary Endpoint: Progression-Free Survival as Adjudicated by IRC

Progression-Free Survival (PFS) time in months, is defined as the time from first administration of study treatment until the first documentation of progression of disease (PD) or death due to any cause, whichever occur first. The tumor response will be determined according to RECIST 1.1 and assessed by the IRC. PFS time will be calculated as follows:

$$PFS \text{ (months)} = \frac{(date \text{ of } PD \text{ or death or censoring} - date \text{ of first dose of study treatment} + 1)}{30.4375}$$

Tumor assessments will be measured at screening and during the intervention period: at week 9 day 57, week 17 day 113, then every 8 weeks (or until disease progression) for 12 months and then every 12 weeks or until disease progression (see Table 1 in the study protocol).

The following censoring rules will also be applied for the PFS computation:

- Participants with no event (PD or death) will be censored on the date of the last adequate tumor assessment
- Participants who do not have a baseline tumor assessment or who do not have any evaluable post-baseline tumor assessments will be censored at the date of first administration of study treatment unless death occurred on or before the time of the second planned tumor assessment (i.e. 17 weeks) in which case the death will be considered an event.
- Participants who start new anticancer treatment prior to an event will be censored on the date of the last evaluable tumor assessment before anticancer therapy is given.

Note: any systemic anticancer therapy, any anticancer surgery and any anticancer radiotherapy will be considered as new/subsequent anticancer therapy and will lead to censoring.

- Participants with an event after two or more subsequent missing response assessments (i.e. no assessments in 113 days prior to the event during the first 12 months [i.e. 365 days of follow-up] or 168 days prior to the event after the first 12 months of follow-up) will be censored on the date of the last evaluable tumor assessment.

The last tumor assessment date is defined as the last available and evaluable tumor assessment performed prior to the cut-off date (or prior to end of study, i.e. participants lost to follow-up or who withdraw consent) or prior to subsequent anticancer therapy.

Censoring rules are summarized in [Table 8](#) and [Table 9](#).

Table 8 Date of Event/Censoring Definition for PFS Analysis

Status		Censoring	Date of event / censoring
Progressed or died	Within two subsequent scheduled tumor assessments after last response assessment of CR, PR or SD receiving the first dose of study treatment	Event	Minimum (Date of PD, Date of death)
	Otherwise	Censored	Date of last tumor assessment with outcome CR, PR or SD or date of first study drug administration, whatever is later.
Neither progressed nor died		Censored	Date of last tumor assessment with outcome CR, PR or SD or date of first study drug administration, whatever is later.

CR=Complete response, PD=Progressive disease, PR=Partial response, SD=Stable disease.

Table 9 Outcome and Event Dates for PFS

Scenario	Date of event/censoring	Outcome
No baseline assessment or no evaluable post-baseline assessment	Treatment start date	Censored ^a
PD or death \leq 16 weeks after last adequate tumor assessment or \leq 16 weeks after start date	Date of PD or death	Event
PD or death after 2 or more missing ^b post-baseline tumor assessments	Date of last adequate tumor assessment ^c documenting no PD before subsequent anti-cancer therapy is given or missed assessments	Censored ^b
No PD	Date of last adequate tumor assessment ^c documenting no PD before [subsequent anti-cancer therapy is given or] missed assessments	Censored
Treatment discontinuation due to 'Disease progression' without documented progression	Not applicable	Information is ignored. Outcome is derived based on documented progression only.
Subsequent anti-cancer therapy given before PD or death event	Date of last adequate tumor assessment ^c documenting no PD before subsequent anti-cancer therapy is given or missed assessments	Censored

PD=Progressive disease.

^a However if the participant dies \leq 17 weeks after start date the death is an event with date on death date.^b Derivation of 2 or more missing tumor assessments according to the following rules:

Last Evaluable Scan Prior to Event (PD or Death), days since treatment start	Censor if Duration Between Last Scan and Event
[Day 1, Day 336]	>56 days (8 weeks)
>Day 337	>84 days (12 weeks)

Scenario	Date of event/censoring	Outcome
----------	-------------------------	---------

^c If there are no adequate post-baseline assessments prior to the PD or death, then the time without adequate assessment should be measured from the start date; if the criteria were met the censoring will be on the start date.

The analysis of PFS as measured by the IRC (secondary endpoint) will be performed with a Kaplan-Meier method (product-limit estimates) and a summary of associated statistics will be presented including corresponding two-sided 95% CIs. The CIs for the median will be calculated according to Brookmeyer and Crowley (1982) and CIs for the survival function estimates will be derived using the log-log transformation according to Kalbfleisch and Prentice (1980) (CONFTYPE = loglog default option in SAS PROC LIFETEST). The estimate of standard error will be computed using Greenwood's formula.

Frequency (number and percentage) of participants with and without event and within each event type (PD or death) will be presented as well as the PFS Med, Min, and Max. Number of participants at risk, failed and PFS rates with their CI at 3, 6, 9, 12, 18 and 24 months will also be provided. Censoring reasons will also be described. Censoring reasons are as follows:

- Ongoing in the study without an event
- No baseline assessment
- No evaluable post-baseline assessment
- Start of new anticancer therapy
- Event after 2 or more missing or non-evaluable post-baseline assessments
- Withdrawal of consent
- Lost to follow-up

Lost to follow-up will include the following participants:

- Lost to follow-up status is collected on the eCRF treatment termination page or eCRF study termination page prior to the analysis cut-off
- Participants with the last alive date > 14 weeks prior to the analysis cut-off date (duration of 14 weeks is based on the assessment schedule of every 3 months for survival follow-up interval + 2-weeks window)

PFS will also be presented graphically with Kaplan-Meier figures.

[figure not shown]
Listing will be provided with the following information: participant identifier, age, sex, race, date of first administration of study treatment, date of last tumor assessment, date of event/censoring, event/censoring reason, time to event. This listing will be sorted by participant identifier.

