- In the case of PD, treatment may continue past the initial determination of PD or confirmed PD if the participant's performance status has remained at least stable, and if in the opinion of the Investigator, the participant will benefit from continued treatment and if other criteria are fulfilled as outlined in the protocol.
- In the case of stable disease, partial response, or complete response, treatment should be continued until the end of 24 months. If the Investigator believes that a participant will benefit from treatment beyond 24 months, it may be permissible after discussion with the Medical Monitor and the Sponsor Medical Responsible.
- Safety Follow-up will continue until 12 weeks after the last dose of bintrafusp alfa. The 12-week Safety Follow-up is allowed to be conducted via telephone calls or patient chart reviews unless there is medical necessity requiring a clinical visit.
- Long-term Follow-up for progression and survival should be performed every 12 weeks after the Safety Follow-up according to the Schedule of Activities. Long-term Follow-up should be performed by patient chart reviews or telephone calls unless a clinical visit is indicated.

Number of Participants:

The planned total sample size is 29 female participants to address the primary and other efficacy objectives, safety assessments, and evaluation of the clinical utility of the RT-PCR-based assay for HMGA2. CCI

Assuming a true objective response rate of 30%, the probability to observe a lower bound of the exact 95% confidence interval above 10% (the benchmark for clinically non-relevant effect) would be 81% when analyzing 29 participants.

Study Intervention Groups and Duration:

[figure not shown]
The planned maximum study duration for a participant is estimated to be up to 24 months (in certain instances, this duration may be lengthened if it is in the best interest of the participant to continue further treatment). This includes a 28-day Screening period (decision will be made in this period for participants' study inclusion if all eligibility criteria are met); a treatment duration until confirmed PD, unacceptable toxicity, study withdrawal or death occurs, a 28-day Safety Follow-up Visit, a 12-week Safety Follow-up phone call after the last dose of bintrafusp alfa, and a Long-term Follow-up (performed every 12 weeks after the Safety Follow-up).

Involvement of Special Committee(s): Yes

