	Day -28 to Treatment Assignment	V1	V2	V3	V4	V5	V6	V7	V8	V9	Until PD	On the Day of or Within 7 Days of Decision to Discontinue	28 Days (± 5 Days) After Last Treatment	12 Weeks (± 2 Weeks) After Last Treatment	Every 12 Weeks (± 2 Weeks)		
		W1	W3	W5	W7	W9	W11	W13	W15	W17							
	D1	D15	D29	D43	D57	D71	D85	D99	D113								
β-hCG pregnancy test		X	X		X		X		X		X	Q4W		X	X ⁱ		β-hCG should be determined from serum at Screening and from a urine or serum sample thereafter. Results of the most recent pregnancy test should be available prior to dosing of study intervention. If a confirmation of a participant's postmenopausal status is necessary, FSH and estradiol tests will be performed at Screening. i: Participants may go to local laboratory to perform pregnancy test. Clinical visit is not required.
T4 and TSH		X			X		X			Q6W			X				

Assessments & Procedures	Pre screening	Screening	Intervention Period (\pm 3 days)										End-of-Treatment Visit	Safety Follow-up Visit		Long-term Follow-up	Notes
	Day -28 to Treatment Assignment	V1	V2	V3	V4	V5	V6	V7	V8	V9	Until PD	On the Day of or Within 7 Days of Decision to Discontinue	28 Days (\pm 5 Days) After Last Treatment	12 Weeks (\pm 2 Weeks) After Last Treatment	Every 12 Weeks (\pm 2 Weeks)		
			W1	W3	W5	W7	W9	W11	W13	W15							
		D1	D15	D29	D43	D57	D71	D85	D99	D113							
+Tumor Assessments																	
Tumor evaluation /staging (CT scan/MRI/other established methods)		X					X					X	Q8W up to 12 months, then Q12W		X ^j	See Section 8.1. j: For participants discontinuing treatment due to reason other than PD, perform tumor evaluation Q8W until 12 months (e.g.W49), then Q12W until confirmed PD or study discontinuation. The window for tumor evaluation is \pm 7 days. The Intervention Period window of (\pm 3 days) is not applicable for tumor evaluations.	
Subsequent anticancer therapy (any line)														X	X	X	
Survival follow-up															X		

Assessments & Procedures	Pre screening	Screening	Intervention Period (± 3 days)										End-of-Treatment Visit	Safety Follow-up Visit		Long-term Follow-up	Notes			
	Day -28 to Treatment Assignment	V1	V2	V3	V4	V5	V6	V7	V8	V9	Until PD	On the Day of or Within 7 Days of Decision to Discontinue	28 Days (± 5 Days) After Last Treatment	12 Weeks (± 2 Weeks) After Last Treatment	Every 12 Weeks (± 2 Weeks)					
		W1	W3	W5	W7	W9	W11	W13	W15	W17			D1	D15	D29	D43	D57	D71	D85	D99
PK, ADA and Biomarker																				

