Approximately 20% of TNBC tumors express PD-L1, although expression is predominantly localized to the tumor-infiltrating lymphocytes ([Mittendorf 2014](#)). Importantly, in the TNBC cohort of the Phase I Study of the anti-PD-L1 drug, atezolizumab, higher PD-L1 expression correlated with improved response to treatment and survival ([Emens 2019](#)). Similarly, in the recent IMPassion130 study of nab-paclitaxel \pm atezolizumab in advanced, treatment-naïve TNBC, 40.9% of participants were determined to be PD-L1 positive and median overall survival (OS) was significantly improved in participants who received chemotherapy plus atezolizumab versus chemotherapy and placebo (25.0 months versus 18.0 months), highlighting the significant contribution of PD-L1 blockade for these participants ([Schmid 2018](#), [Schmid 2019](#)).

Bintrafusp alfa has shown promising clinical activity in participants with TNBC in the expansion cohort of the Phase I Study EMR200647-001 ([Spira 2019](#)). As of 15 October 2019, participants (n= 33) with heavily pretreated TNBC (54.5% of participants had ≥ 4 prior regimens) received a median of 3 (range 1 to 24) doses of bintrafusp alfa (1200 mg every 2 weeks). Responses as assessed by Investigator occurred in 4 participants; 3 of 4 responses were confirmed by Independent Review Committee (IRC), while the fourth was considered stable disease (SD). The objective response rate (ORR) for these 4 responses was 12.1% (95% confidence interval [CI]: 3.4, 28.2) and disease control was achieved in a total of 5 participants (15.2% [95% CI: 5.1, 31.9]) per Investigator. The median OS was 7.8 months (95% CI: 2.1, 12.8). PD-L1 expression in tumor cells or in the tumor microenvironment was not associated with response to treatment. Bintrafusp alfa was well tolerated, with a safety profile consistent with expectations in this heavily pretreated, advanced TNBC cohort.

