4.1 Overall Design

This is a Phase II, multicenter, single-arm, open label study to evaluate bintrafusp alfa monotherapy in participants with TNBC who express high levels of HMGA2 as determined by a centralized reverse transcriptase-polymerase chain reaction (RT-PCR) test with predefined cutoff. Participants must have progressed during or after first-line of chemotherapy.

The primary objective is to evaluate the clinical efficacy of bintrafusp alfa based on the ORR as assessed by an IRC. The key secondary objectives are duration of response (DOR), durable response rate (DRR), progression-free survival (PFS), OS, and safety. Tumor response evaluations based on Response Evaluation Criteria in Solid Tumors Version 1.1 (RECIST 1.1) ([Eisenhauer 2009](#)) will be performed every 8 weeks until 12 months after the first administration of bintrafusp alfa and then every 12 weeks until confirmed disease progression, unacceptable toxicity, or occurrence of any criterion for withdrawal from the study.

The study plans to enroll approximately 29 eligible participants globally with competitive enrollment.

The study includes:

- Prescreening (a Prescreening informed consent form [ICF] will be used for HMGA2 biomarker analysis and collection of baseline clinical history). Positive HMGA2 test results on tumor tissue is required to enter formal study Screening (see [Table 1](#)).
- Up to 28-day Screening period.
- Treatment with bintrafusp alfa at a dose of 1200 mg intravenously once every 2 weeks until confirmed PD, unacceptable toxicity, study withdrawal, or death.
- In the case of PD, treatment may continue past the initial determination of PD or confirmed PD, if the participant's performance status (PS) has remained at least stable, and if in the opinion of the Investigator, the participant will benefit from continued treatment and if other criteria are fulfilled as outlined in the protocol (see [Section 7.1.3](#)).
- In the case of SD, PR, or complete response (CR), treatment should be continued until the end of 24 months. If the Investigator believes that a participant will benefit from treatment beyond 24 months, it may be permissible after discussion with the Medical Monitor and the Sponsor Medical Responsible.
- Safety Follow-up will continue until 12 weeks after the last dose of bintrafusp alfa. The 12-week Safety Follow-up is allowed to be conducted via telephone calls or patient chart reviews, unless there is medical necessity requiring a clinical visit.

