6.9.6.2 Embryofetal Toxicity

Embryofetal toxicities are a known risk of the PD-1/PD-L1 targeting class and are considered important potential risks for bintrafusp alfa. Animal models link the PD-1/PD-L1 signaling pathway with maintenance of pregnancy through induction of maternal immune tolerance to fetal tissue. An appropriate contraception warning is provided as part of the inclusion criteria. Pregnant and breastfeeding women are not allowed in the bintrafusp alfa study, and adequate contraceptive measures are recommended during the study to minimize or eliminate the potential risk to the developing fetus.

Respective safety measures comprise of inclusion/exclusion criteria for participation in clinical studies with bintrafusp alfa, guidance for prevention, monitoring, and medical management of potential risks, as well as guidance on study intervention interruption or discontinuation.

7**Discontinuation of Study Intervention and Participant Discontinuation/Withdrawal****7.1****Discontinuation of Study Intervention**

Participants may be discontinued from study intervention for any of the following reasons, one reinitiating course of treatment may be allowed (see Section 7.1.2.1).

- A participant may discontinue from the study intervention at any time at his/her own request (i.e., withdrawal of consent), and without giving a reason.
- Occurrence of an exclusion criterion, which is clinically relevant and affects the participant's safety, if discontinuation is considered necessary by the Investigator and/or Sponsor.
- A participant may be discontinued at any time at the discretion of the Investigator for safety, behavioral, compliance, or administrative reasons (See Section 6.8 and Section 6.9 for TEAEs and AESIs that require treatment discontinuation, respectively).
- PD per RECIST 1.1 plus subsequent confirmation (repeat imaging 4 to 6 weeks after initial determination of PD), with the exception that participants receiving treatment may continue past PD if the participant's ECOG PS has remained at least stable, and, if in the opinion of the Investigator, the participant may benefit from continued treatment (see Section 7.1.3). A participant with significant symptomatic disease progression and/or clinical deterioration should be discontinued prior to confirmation of PD per RECIST 1.1.
- Unacceptable toxicity
- Some TEAEs and AESIs require withdrawal from treatment. See Section 6.8 and Section 6.9 for additional details.

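### Clinical progression before the first evaluable scan can be censored from PFS at Day 1, and no visible sensitivity analysis shows the effect

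*SAP*

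**What the plan says.** **PFS rules.** SAP 14.1.1 does not accept clinical deterioration as documented progression. For PFS, SAP Table 9 has a row for participants who stop treatment because of disease progression that was never documented: "Information is ignored. Outcome is derived based on documented progression only". SAP 14.4 adds that a participant with no baseline scan or no evaluable post-baseline scan "will be censored at the date of first administration of study treatment unless death occurred on or before the time of the second planned tumor" (the sentence goes on to put that scan at 17 weeks). Table 9 footnote a repeats the death exception, and Protocol Table 11 has the same rule. A participant who starts new anticancer treatment before an event is censored at the last evaluable scan before that treatment. Where there is none, Table 8 falls back to the date of first dose.

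**Scan timing.** SAP 14.4 puts the first two on-study scans at Day 57 (Week 9) and Day 113 (Week 17).

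**Sensitivity analysis.** The only one visible, SAP 14.4.1, repeats PFS on the Investigator's read under the same Tables 8 and 9. The text after it is redacted.

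**ORR.** SAP 14.1.1 names the same group, "Participants who do not have an on-treatment radiographic tumor assessment due to early progression", and counts them as non-responders.

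**Imaging after a stop.** Note j of the Schedule of Activities reads "For participants discontinuing treatment due to reason other than PD, perform tumor evaluation Q8W until 12 months", then every 12 weeks. Protocol 8.1 schedules scans for participants generally through Long-term Follow-up and states no exception. Protocol 4.1 has scans every 8 weeks to 12 months, "then every 12 weeks until confirmed disease progression, unacceptable toxicity, or occurrence of any criterion for withdrawal from the study".

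**The concern.** Take a participant who deteriorates at Week 5, is taken off treatment for progression, and has no scan before starting another therapy. The trial team regards the treatment as having failed, and ORR records a failure. PFS records no event and no follow-up time: the participant leaves the risk set before the curve begins.

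That is informative censoring, because the people removed are those who progressed fastest. There is no control arm in which the same bias could partly cancel, so any excess goes directly into the PFS estimate and into any comparison with outside figures. PFS is a key secondary endpoint, and Protocol 9.4.4 uses it to support the efficacy assessment. Because the Investigator-read analysis inherits the same rules, agreement between the two curves would give no reassurance on this point.

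**Working it through.** **Inputs**
- N = 29, single arm: "The planned total sample size is 29 female participants" (Protocol 1.1).
- First scans on Day 57 and Day 113; death exception to 17 weeks, taken as Day 119 (SAP 14.4).
- Phase I median OS 7.8 months, 95% CI 2.1 to 12.8 (Protocol 2.2).
- c, the number censored at Day 1 by this route: not in the documents, so assumed.

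**The plan's own figure.** The plan states no precision or target for PFS. Its one design figure is for ORR: 81% probability that the exact lower limit exceeds 10% when the true rate is 30%. The smallest qualifying count is 7 of 29 (lower limit 10.3%), and the exact probability of 7 or more is 81.2%. The figure reproduces. It is untouched here, because these participants stay in the ORR denominator as non-responders.

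**Effect on Kaplan-Meier.** A participant censored at Day 1 leaves before any event. Let k be the number progression-free at a time after the early exits, with no other early censoring.
- Plan as written: S = k/(29-c).
- Exits counted as events: S = k/29.
- Ratio: 29/(29-c).

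| c | ratio | S as written if k = 10 (10/29 = 34.5%) |
|---|---|---|
| 3 | 29/26 = 1.12 | 10/26 = 38.5% |
| 5 | 29/24 = 1.21 | 10/24 = 41.7% |
| 8 | 29/21 = 1.38 | 10/21 = 47.6% |

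The choice k = 10 is only an illustration. The ratio does not depend on it.

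**Death exception.** Suppose 6 participants stop unscanned and none starts new therapy. If 0, 2, 4 or 6 of them die by Week 17, c is 6, 4, 2 or 0. With k = 10 the estimate is 10/23 = 43.5%, 10/25 = 40.0%, 10/27 = 37.0% or 34.5%. To gauge how often the exception applies, assume exponential OS: P(death by Day 119) = 1 - exp(-ln 2 × 3.91/m), with 119/30.4375 = 3.91 months and m the median OS. This gives 29% at m = 7.8, 19% at 12.8 and 72% at 2.1. Early failures probably die sooner than the average participant. A death that does count is dated at death, not at clinical progression, so the early curve still sits somewhat high.

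**Two unsettled rules that change c.** The SAP does not say which takes precedence when new therapy is followed by death before Week 17. Table 9 footnotes b and c, read literally, censor at the start date once the gap from start exceeds 56 days. That conflicts with footnote a (17 weeks), the 16-week row and the 113-day text, and could remove deaths on about Day 58 to Day 119.

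**The case against.** The case on the other side is substantial, and much of it stands.

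- **Imaging.** A reader might infer that these participants are excused from further scans. No passage says so. Protocol 8.1 schedules scans through Long-term Follow-up, and if PD means RECIST PD, a symptomatic stop is itself a stop for another reason, so note j would continue scans. A scan showing PD within 16 weeks of start is an event. What remains is a conflict of wording. It does not help the participant who starts new therapy before Week 9, whom later imaging cannot recover.
- **Protocol 7.1.** The sentence "A participant with significant symptomatic disease progression and/or clinical deterioration should be discontinued prior to confirmation of PD per RECIST 1.1" might be read as directing a stop before any scan. It closes the bullet on RECIST PD with repeat imaging, so it can equally mean stopping between the initial and confirmatory PD scans, in which case PD is already documented. Other grounds in 7.1 do allow a stop before any scan.
- **Frequency.** Phase I participants "received a median of 3 (range 1 to 24) doses of bintrafusp alfa" (Protocol 2.2). On a 2-week schedule the third dose falls on Day 29, and a reader might infer that leaving before Week 9 unscanned is common. Neither scan timing nor reasons for stopping are given, so this shows plausibility and no rate. In the same section, 1 of 8 HMGA2-high participants was non-evaluable, reason not stated. Scaled, 29 × 1/8 = 3.6, a ratio of about 1.14 before the death exception, from a very small sample.
- **ORR against PFS.** The different handling is not an inconsistency in itself. A binary rate must classify everyone, while a time-to-event endpoint may censor.
- **Endpoint integrity.** PFS is defined by RECIST 1.1 and IRC read. Counting symptomatic stops brings in open-label judgement. That is a good reason to leave the main analysis alone, and no reason to omit a sensitivity analysis.
- **Transparency.** SAP 14.4 tabulates censoring reasons, including no evaluable post-baseline scan, and SAP 10.1 tabulates stops for progression. The two are not crossed, so c cannot be read from the tables. A further sensitivity analysis in the redacted text cannot be ruled out.

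**Conclusion.** The point holds for a defined group: participants who stop for clinical progression before any evaluable post-baseline scan and who either survive past Week 17 or start new therapy first. They are censored at Day 1, and at times after these exits PFS is raised by 29/(29-c) relative to counting them as events. The direction is certain whenever c > 0. The size rests on an assumed c and on no other early censoring.

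A reader might infer that all early failures vanish from PFS. They do not, because deaths by Week 17 are meant to count as events. A reader might also infer that this trial's reported PFS is inflated. SAP 4.1 says no efficacy analyses will be performed after the early discontinuation, so under version 2.0 there is no realised effect. This is a weakness in the written plan for a secondary endpoint, cheap to correct, and the primary endpoint is not involved.

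Separately, note j, Protocol 8.1 and Protocol 4.1 do not agree on who continues to be scanned after stopping. Protocol 4.1 ends scans at unacceptable toxicity, whereas note j continues them for stops other than PD.

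**What to change.** 1. **SAP 14.4.1.** Add a PFS sensitivity analysis that counts discontinuation for progressive disease without documented PD as an event on the discontinuation date. Report the number so classified beside the main PFS. Keep the IRC RECIST analysis as it is.
2. **Protocol.** Reconcile note j, section 8.1 and section 4.1 so that it is clear whether the scheduled scans continue for participants who stop without RECIST-documented PD, and for those who stop for toxicity. Which rule to adopt is for the sponsor to decide.

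Cost: one further Kaplan-Meier run on discontinuation reasons already collected in the eCRF, and rewording of three imaging passages. The SAP change needs no extra procedure for participants. The downside is that the sensitivity PFS relies on open-label investigator judgement and will be less favourable than the main estimate. With efficacy analyses now cancelled, the change matters if those analyses are ever run or the plan is reused.
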